Contrasting Ketogenic and Mediterranean Diets in Individuals with Type 2 Diabetes and Prediabetes: The Keto-Med Trial

NCT #: 03810378

Date: 12/18/20

Statistical Analysis Plan for The Keto-Med Trial

Contrasting Ketogenic and Mediterranean Diets in Individuals With Type 2 Diabetes and Prediabetes

* (CGM) - to be worn for a two-week interval at each time as indicated by the thick border

Background

The proposed randomized clinical trial will investigate differential population-specific effects of two low-carbohydrate (low-carb) diet patterns, addressing a gap in the evidence base in this area that will lead to 1) improved treatment strategies for common adverse clinical conditions, 2) improved health for these individuals, and 3) long-term decreases in health care costs. This impactful research will advance the field of personalized and precision medicine.

A Mediterranean Diet (Med-Plus), as defined in this study, maximizes the intake of vegetables, legumes, fruits and nuts, whole intact grains/cereals and fish; and minimizes the intake of meat, poultry, and dairy. This diet should exclude added sugars and refined grains.

A Well-Formulated Ketogenic Diet (WFKD) diet, as defined in this study, maximizes the intake of non-processed beef, pork, and poultry (preferably organic/grass-fed), fish, heavy cream, low-lactose, high-fat cheeses, animal fats, oils (avocado, coconut, or other nut oils), non-starchy (above ground) vegetables and limited amounts of some fruits (berries). This diet should exclude legumes, grains, sugars, starchy (below ground) vegetables, most fruits, and polyunsaturated oils (soy, sunflower, peanut, cottonseed, canola, etc.). Furthermore, this diet will aim for an intake of 20 g of carbohydrates/day at start, with the goal to have no more than 50 grams/day to maintain ketosis.

The objective of the current study is to contrast the potential beneficial and adverse health consequences of two metabolically distinct diets: Well-Formulated Ketogenic Diet (WFKD) vs Mediterranean Diet (Med-Plus), in a crossover design among generally healthy adults.

Study Design:

This cross-over study aims to investigate the impact of two metabolically distinct diets on Glycated hemoglobin, cardiovascular health, the gut microbiome, and metabolic status. Participants are recruited using media advertisements, email lists, and clinician referral ([name]) from previous recruitment for nutrition studies conducted by our laboratory group. Forty participants are planned to be randomized between the two arms: (1) start with 12 week WFKD and switch to 12 week Med-Plus; (2) start with 12 week Med-Plus and switch to 12 week WFKD. Randomization will be stratified by diabetes vs pre-diabetes status. As displayed in figure above, clinical and metabolic measurements are taken at baseline, and weeks 0, 6, 12, (Phase I, weeks 1-12), 18, 24 (Phase II, weeks 13-24) and 36 (Maintenance Phase). Continuous glucose monitoring will be collected five times during the trial, each time data will be collected every hour for ten days.

Primary Outcome:

• Difference in percent difference from baseline after 12 weeks of each phase

Secondary Outcomes:

- Difference in percent difference from baseline in LDL cholesterol after 12 weeks of each phase
- Difference in percent difference from baseline in HDL cholesterol after 12 weeks of each phase
- Difference in percent difference from baseline in triglycerides after 12 weeks of each phase
- Difference in percent difference from baseline in fasting insulin after 12 weeks of each phase
- Difference in percent difference from baseline in blood pressure after 12 weeks of each phase
- Difference in percent difference from baseline in weight after 12 weeks of each phase
- Difference in percent difference from baseline in alpha diversity after 12 weeks of each phase. Primary metric of alpha diversity will be using number of observed sequence variants ("species") determined by standard 16S rRNA amplicon sequencing (V3-V5 region followed by DADA2 to define error-corrected sequence variants). *Note: Higher alpha diversity is better. The units are the # of sequence variants*
- Difference in percent difference from baseline in composite of short-chain fatty acids (SCFA) concentration (ug/g stool: acetate + propionate + butyrate) after 12 weeks of each phase

Exploratory outcomes:

- Difference in satisfaction with WFKD and Med-Plus diets, using a 5-point Likert scale (1=not at all satisfied; 2=slightly satisfied; 3=moderately satisfied; 4=very satisfied; 5=extremely satisfied).
- Difference in adherence to diet protocols by diabetes vs. pre-diabetes status, according to 3day food records.
- Tabulate COVID-19 Survey answers

Primary Analysis

Patient demographics and baseline clinical characteristics will be summarized by arm, as n (%) and median (interquartile range) for categorical and continuous variables, respectively. To assess any differences in each variable between the two arms, the absolute standardized differences are presented, where a value of 0.2 or less, 0.5, and 0.8 or more correspond to small, medium, and large differences, respectively. Characteristics found to display large differences will be adjusted for in a sensitivity analysis. We will also compare rate of adherence for WFKD after 12 weeks and Med-Plus diets after 12 weeks using a Fisher's Exact test with weekly NDSR (and Cronometer) data. We will develop a composite score to measure a participant's adherence to each diet.

We will use a mixed-effects linear model (1) with HbA1c percent difference from baseline for diet, j, as the outcome. We want to assess for a difference in diet (WFKD vs Med-Plus), while adjusting for fixed effects: order (e.g. study arm), pre-diabetes vs. diabetes status, and a random effect for each participant, i.

$$\left(\frac{HbA1c_{ij}-HbA1c_{i0}}{HbA1c_{i0}}\right) = \beta_o + \beta_1 Order_i + \beta_2 Diabetes_i + \beta_3 Diet_{ij} + \gamma_i$$
(1)

For the primary outcome, we will use a two-sided likelihood ratio test to test for no difference between diet types. The primary analysis will include participants with baseline blood draws, and at least one blood draw in each phase (including crossing over). The primary analysis will be a complete case analysis and use participants' last available lab values in each phase or week 12, if available; patients who did not complete both phases (i.e. crossover) will be excluded. A significance level of 0.05 is set for all analyses. In a sensitivity analysis, we will adjust for baseline weight and percent weight change if weight change from baseline is found to be significant, since this is known to impact HbA1c values; and in a separate analysis, we will adjust for adherence to each diet.

Similarly, for our secondary outcomes, we will use separate mixed-effects models to evaluate fasting lipids, insulin, glucose, blood pressure and short-chain fatty acids for WFKD vs Med-Plus, adjusting for order, phase, pre-diabetes vs. diabetes status, and repeated measures. A two-sided likelihood ratio test will be used to assess no difference between diet types. For our exploratory outcome comparing diet satisfaction, we will use a Wilcoxon signed-rank test to evaluate the null hypothesis that the difference between pairs follows a symmetric distribution around zero, which indicates similar satisfaction with both diets. We will use a Fisher's Exact test to evaluate any difference in the rate of adherence due to diabetes vs pre-diabetes status, within each diet.

Sensitivity Analysis

Due to COVID-19, visits to collect blood draws were delayed for some participants. These participants report they maintained the phase's diet until the lab measurements could be collected. We will check adherence to diet based on NDSR at Week 12 and Week 12 extra visit (taken when allowed back into clinic), and also check for a change in dietary and exercise habits during shelter-in-place. Potential impact of delays are unclear; subsequently, we will perform a number of sensitivity analyses:

Sensitivity Analysis 1 (SA1): For a simple truncated analysis, we will consider only the first phase (12 weeks) of each group and compare differences (two-sample)

Sensitivity Analysis 2 (SA2): For a simple estimate of Week 12 analysis, we will consider the average of the last lab measurement of each 12 week phase and the extra data point at Week 12 extra visit.

Sensitivity Analysis 3 (SA3): For an extended-phase analysis, we will consider using the last lab measurement from each phase, i.e. the "extra" data timepoints after week 12 in study for some participants.

Sensitivity Analysis 4 (SA4): For a pre-COVID-19 truncated analysis, we will consider the subset of data prior to the official Shelter-in-Place date for the Bay Area, March 16, 2020.

Sensitivity Analysis 5 (SA5): To assess any effect on outcomes due to COVID-19 impact on logistics, we will consider the subset of data when participants received groceries for each diet. We will also evaluate if adherence was better for the first four weeks when groceries were delivered.

Secondary Analysis

For our secondary analysis, we want to investigate: (a) a potential difference in the primary outcome by diabetes status; (b) the different trajectories of each diet; and (c) different metrics using continuous glucose monitoring data and how that compares with the gold standard HbA1c data. In a low-power analysis for (a), we will use model (1) and include an interaction term for diet and diabetes status. For (b), we will use all time points in a model similar to (1) but with a time variable. Lastly for our analysis in (c), we will consider different metrics used in the literature for continuous glucose monitoring and compare trajectories of each metric with that of the gold standard using HbA1c data.

Exploratory Analysis

For our exploratory analysis, we want to investigate long term maintenance. Upon completing both diet phases, for three months participants were instructed to eat the diet of their choosing. This analysis will be largely descriptive on what participants were consuming and their change in lab measurements.

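### Phase I weight change that persists after the direct diet switch is credited to the second diet, and no planned analysis is named as the check for it

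*SAP*

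**What the plan says.** - **Design (SAP, Study Design).** "Forty participants are planned to be randomized between the two arms", with the sequences given as "1) start with 12 week WFKD and switch to 12 week Med-Plus; (2) start with 12 week Med-Plus and switch to 12 week WFKD". The timing is "Phase I, weeks 1-12), 18, 24 (Phase II, weeks 13-24", so Phase II starts the week after Phase I ends.
- **Weight (SAP, Secondary Outcomes).** The endpoint is the "Difference in percent difference from baseline in weight after 12 weeks of each phase".
- **Primary model (SAP, Primary Analysis).** Model (1) takes "HbA1c percent difference from baseline for diet, j, as the outcome". Its reference value carries a participant index and no phase index, so both diets share one baseline. The terms are Order, diabetes status, diet and a random participant effect; there is no phase term. Only participants with data in both phases are analysed.
- **Secondary models (same section).** These are fitted "adjusting for order, phase, pre-diabetes vs. diabetes status, and repeated measures". The outcomes named there are lipids, glucose, insulin, SCFAs and blood pressure. Weight is not among them.
- **Weight and HbA1c (same section).** The SAP states that weight change influences HbA1c. It plans to adjust for baseline weight and percent weight change in a sensitivity analysis, if weight change proves significant.
- **SA1 (SAP, Sensitivity Analysis).** This is a two-sample comparison of the first phase only. The reason given for the whole set of sensitivity analyses is "Potential impact of delays are unclear; subsequently, we will perform a number of sensitivity analyses".

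The SAP does not mention carry-over.

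**The concern.** Weight accumulates. A participant who loses weight on the first diet starts the second diet lighter. If some of that loss is still there at week 24, the Phase II score is the second diet's effect plus the remainder of the first diet's effect, and the model assigns the whole of it to the second diet.

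Two conclusions are at stake. A finding of no difference in weight could partly reflect attenuation. A finding of a difference could partly reflect that the loss on one diet lasts longer than the loss on the other. By the SAP's own statement about weight, the concern extends to the primary outcome, HbA1c.

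**Working it through.** **Inputs from the SAP.** 40 participants, two sequences, no gap between phases, one baseline, complete pairs, two-sided test at 0.05. The SAP gives no effect size, SD or retained share for weight, so there is no planned figure to reproduce. All such values below are assumptions.

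**Notation.** K and M are the true 12-week percent changes on WFKD and Med-Plus. rK and rM are the shares of the Phase I change on each diet still present at the end of Phase II. Phase II is taken to add its full effect to what remains. With complete pairs, the model (1) diet estimate is the mean within-participant difference, WFKD minus Med-Plus.

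**Step 1: equal retention (rK = rM = r).**
- WFKD first: K − (M + rK)
- Med-Plus first: (K + rM) − M
- Mean over balanced sequences: (1 − r/2)(K − M)

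Assume K = −8 and M = −6, so the true difference is −2.0 points. Power is simulated for the phase-adjusted test with SD 4, within-person correlation 0.6 and 20 per sequence.

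| r | Expected estimate | Share of truth | Power |
|---|---|---|---|
| 0 | −2.00 | 100% | 93% |
| 0.25 | −1.75 | 87.5% | not run |
| 0.5 | −1.50 | 75% | 73% |
| 0.75 | −1.25 | 62.5% | not run |
| 1 | −1.00 | 50% | 40% |

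**Step 2: unequal retention, equal diets (K = M = e).** The mean of the two sequences is (rM − rK)e/2. With e = −6, rK = 0.25 and rM = 0.75, this is 0.5 × (−6)/2 = −1.5 points, an apparent WFKD advantage that does not exist. Exchanging the two shares gives +1.5. A phase term does not change either value. Simulated rejection at nominal 5% (SD 4, correlation 0.6, 20 per sequence) was 53% without phase and 74% with it.

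**Step 3: the Order term.** Order is constant within a participant, so it cancels from every within-participant difference. In one simulated data set with 16 and 20 completers, the diet estimate was −2.727 with and without Order and diabetes status, identical to the mean within-person difference.

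**Step 4: the missing phase term in model (1).** With equal retention, equal diets of effect e, and n1 (WFKD first) and n2 (Med-Plus first) completers, the expected estimate is r·e·(n2 − n1)/(n1 + n2). For e = −6, n1 = 16 and n2 = 20:
- r = 0.5: 0.5 × (−6) × 4/36 = −0.33
- r = 1: 1 × (−6) × 4/36 = −0.67

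Adding phase returns both to 0. This bias did not raise rejection above 5%, because the omitted phase shift also inflates the residual variance. That inflation costs power. In the Step 1 setting the test without phase had 45% power at r = 0.5 and 0.5% at r = 1, against 73% and 40% with phase.

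**Step 5: Phase I alone.** The between-arm difference at week 12 has expectation K − M whatever rK and rM are. Its power for 2 points with 20 per arm, without baseline adjustment, is 56%, 35% and 24% at assumed SDs of 3, 4 and 5.

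**The case against.** The strongest reply is that the plan already contains partial guards and that the size of the problem is assumed.

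- **SA1** is a Phase-I-only comparison and is not restricted to participants with delayed visits. That is true, and the fix builds on it. As written, however, it is tied to COVID-19 delays, is not assigned to weight, is not adjusted for baseline, and has no stated bearing on the crossover conclusion.
- **The weight-adjusted HbA1c analysis** addresses the link through weight. It is conditional on a significant weight change, and it adjusts for a post-randomization variable that itself contains the carry-over.
- **The trajectory model** in Secondary Analysis uses all time points. It is described only as similar to model (1) with a time variable, and no term there separates the first diet's remaining effect.
- **Order** does respond to unequal carry-over. In the Step 2 example its expected coefficient is (0.25 × (−6) − 0.75 × (−6))/2 = 1.5 points, as large as the bias. The SAP does not plan to interpret it, though, and it is a between-participant quantity that would be estimated imprecisely.

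Some stronger readings are not supported. A reader might infer that the weight contrast is halved; that needs all of the Phase I change to persist while Phase II adds its full effect. A reader might infer that the SAP relies on Order to control carry-over; it never says so. A reader might also fix the baseline at week 0. The SAP lists baseline and week 0 separately, but the argument is the same for any single pre-Phase-I value.

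**Conclusion.** The concern holds in conditional form. The direct switch and the single baseline are in the text, and together they credit any persisting Phase I weight change to the second diet. With equal retention r and balanced sequences the contrast shrinks to (1 − r/2) of its true value, a loss of 25% at r = 0.5 and at most 50%. With diet-specific retention a false difference of (rM − rK)e/2 arises, which phase adjustment does not remove. With equal retention and phase in the model there is no false difference. Whether retention is large, or differs by diet, cannot be learned from the SAP.

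For HbA1c the concern applies only as far as weight drives it, and the SAP gives nothing from which to compute a size. Separately, model (1) has no phase term, and weight is missing from the outcomes listed for the phase-adjusted models.

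A reader might conclude that the crossover weight result should be set aside in favour of Phase I. The figures do not support that. At SD 4 the Phase I contrast has about 35% power, against 73% for the phase-adjusted crossover at half retention and 40% even at full retention.

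**What to change.** 1. Keep the crossover estimate as planned.
2. Extend SA1 into the named carry-over check for weight and HbA1c: week 12 compared between arms, adjusted for the baseline value and diabetes status, in all participants with Phase I data and regardless of COVID-19 delays. Report it beside the crossover estimate.
3. Show the within-participant diet difference separately for each order.
4. Add phase to model (1), and list weight among the outcomes of the phase-adjusted models.
5. State in advance that a crossover weight result that disagrees with Phase I, or that differs by order, will be interpreted as possibly affected by carry-over.

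Re-baselining Phase II at week 12 is a tempting alternative but not a general cure. Its expectation is (1.5 − r/2)(K − M), which is right only at r = 1 and is 1.5 times too large at r = 0.

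The cost is SAP wording and a few extra models on data already collected. The drawback is that the Phase I estimate has a much wider interval (24% to 56% power for an assumed 2-point difference at SD 5 to 3). Disagreement with the crossover can therefore arise by chance, and agreement is weak reassurance.

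### Adjusting model (1) for baseline differences between the sequence arms cannot change the diet estimate, so it is not a robustness check; the adjustment belongs in SA1, where no covariates are named

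*SAP*

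**What the plan says.** The arms are sequences, not diets (SAP, Study Design): "1) start with 12 week WFKD and switch to 12 week Med-Plus; (2) start with 12 week Med-Plus and switch to 12 week WFKD". The same section gives the size: "Forty participants are planned to be randomized between the two arms", stratified by diabetes versus pre-diabetes.

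The Primary Analysis section summarises baseline characteristics by arm with absolute standardised differences, "where a value of 0.2 or less, 0.5, and 0.8 or more correspond to small, medium, and large differences, respectively". It then sets the rule: "Characteristics found to display large differences will be adjusted for in a sensitivity analysis". The sentence does not name the model that receives the adjustment.

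The same section defines model (1), with diet as the effect of interest, "adjusting for fixed effects: order (e.g. study arm), pre-diabetes vs. diabetes status, and a random effect for each participant, i". On the data used: "The primary analysis will be a complete case analysis and use participants' last available lab values in each phase or week 12, if available"; and "patients who did not complete both phases (i.e. crossover) will be excluded".

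In the Sensitivity Analysis section, SA1 is a simple truncated analysis: "we will consider only the first phase (12 weeks) of each group and compare differences (two-sample"). No covariate is named for it, not even the randomisation stratum.

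**The concern.** The adjustment rule stands in the Primary Analysis section beside model (1), so a reader would take it as a check on the primary diet result. That result is a within-person contrast. Each participant is their own control, and imbalance between the sequence arms in a fixed characteristic is already removed from it. Adding the characteristic to the model returns the same diet estimate whatever the data show.

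Two things are at stake. First, a statement that the diet effect was unchanged after adjustment for imbalanced characteristics could be read as support for the primary finding, although it carries no information. Second, Phase I alone is a between-person comparison, and there a chance imbalance passes straight into the diet contrast. SA1 is the analysis a reader would turn to if second-phase data were doubted because of carryover or COVID-19 disruption, and the SAP specifies no covariates for it.

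**Working it through.** The SAP states no effect size, standard deviation or power for this analysis, so there is no figure of its own to reproduce. The check is algebra, supported by simulation.

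**Inputs from the SAP.** Two sequence arms, 40 participants planned, complete pairs only, one value per diet per participant, random participant intercept, two-sided likelihood-ratio test for diet, and a trigger of 0.8.

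**Assumed, because the SAP does not give them.** Allocation 20:20 (18:15 also tried), true diet effect -2, covariate slope 2 per SD, participant SD 5 (also 0), residual SD 4.

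**Step 1: algebra for model (1).** For participant i, let d_i be the WFKD value minus the Med-Plus value, and m_i the mean of the two.

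- d_i has mean β3 and variance 2σ². Order, diabetes status, γ_i and any baseline characteristic cancel.
- m_i has variance τ² + σ²/2 and carries the intercept, order, diabetes status and any baseline characteristic.
- d_i and m_i are uncorrelated, so the likelihood splits into two parts.

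Hence the estimate of β3 is the mean of d_i, with or without the covariate. With the variances free, the likelihood-ratio statistic is n × log[Σd_i² / Σ(d_i − d̄)²], which also contains no covariate. The imbalance can change the order coefficient, but not the diet coefficient. The one exception is the constraint τ² ≥ 0. If it binds in any of the fits, the two variances are tied together and the covariate can enter the test, though still not the estimate.

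**Step 2: simulation.** Model (1) was fitted by maximum likelihood with and without a prognostic baseline covariate shifted by 0.8 SD between arms, in 200 trials per scenario.

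| Scenario | Largest change in β3 | Largest change in LRT statistic |
|---|---|---|
| 20:20, complete pairs | 1.1e-14 | 2.3e-13 |
| 18:15, complete pairs | 1.2e-14 | 1.7e-13 |
| 20:20, complete pairs, participant SD 0 | 1.4e-14 | 3.8 |
| 20:20, 6 of 40 lacking Phase II but kept | 0.30 | 1.5 |

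The first two rows are zero to rounding. The third is the boundary case. The fourth breaks the pairing, which the primary analysis does not allow.

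**Step 3: the same covariate in SA1.** Expected shift = slope × imbalance = 2 × 0.8 = 1.6, so the unadjusted contrast should be near -2 − 1.6 = -3.6. Simulated means:

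- 20:20: -3.66 unadjusted, -1.93 adjusted.
- 18:15: -3.50 unadjusted, -2.07 adjusted.

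Without a slope, shift in outcome SD = imbalance × correlation. The standard error of a two-sample difference with 20 per arm is √(2/20) = 0.316 SD.

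| Assumed correlation | Shift (outcome SD) | Shift in standard errors |
|---|---|---|
| 0.1 | 0.8 × 0.1 = 0.08 | 0.25 |
| 0.3 | 0.8 × 0.3 = 0.24 | 0.76 |
| 0.5 | 0.8 × 0.5 = 0.40 | 1.26 |

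**Step 4: how often the rule triggers.** With 20 per arm, a standardised difference of 0.8 corresponds to t = 0.8 × √(20/2) = 2.53 on 38 degrees of freedom, two-sided probability 0.0157. For at least one of k independent characteristics the probability is 1 − (1 − 0.0157)^k: 15% for k = 10 and 27% for k = 20.

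**The case against.** The strongest reply is that the rule names no model. SA1 is itself a sensitivity analysis, so the sentence could be meant for it. This stands in part: a reader might infer that the SAP rules out adjusting SA1, and it does not. It leaves the matter unspecified. But the sentence sits beside model (1), and nothing directs it to SA1.

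A reader might also infer that SA1 is the only analysis exposed to imbalance. The SAP does not support that. SA4 cuts the data at March 16, 2020, and the Secondary Analysis trajectory model uses all time points. Neither says whether the both-phases exclusion is applied again. If incomplete pairs are kept, a baseline covariate can move the diet estimate, as the fourth simulated scenario shows.

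It can further be said that randomisation keeps the unadjusted SA1 contrast unbiased on average. That is correct. The problem is chance imbalance in the trial at hand, and its size here rests on an assumed slope or correlation.

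Finally, the redundant adjustment harms nothing in the primary analysis, the trigger is uncommon for any one characteristic, and the SAP nowhere says how an unchanged result will be interpreted. All true. These points limit the importance of the issue; they do not make the check informative.

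**Conclusion.** The point holds in a limited form. With main-effect adjustment of model (1) in complete pairs, the rule cannot change the diet estimate. This is exact and does not depend on the simulated values. The likelihood-ratio test is also unchanged, except when the participant variance is estimated at zero. A covariate-by-diet interaction would escape the result, but the SAP plans one only for diabetes status.

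The primary estimate and its test are not in error. What is lost is the value of one planned check, together with a specified adjustment for SA1, where an imbalance at the trigger would matter by roughly a quarter to one and a quarter standard errors over the assumed correlations of 0.1 to 0.5. It would be too strong to call SA1 biased by design, or to say that a false claim of robustness is planned. Nothing here shows that the 0.8 threshold is wrong.

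**What to change.** Replace the sentence with text to this effect:

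- SA1 is a covariate-adjusted Phase I comparison of the arms that includes the baseline value of the outcome and diabetes status (the randomisation stratum).
- Any other characteristic with an absolute standardised difference of 0.8 or more between arms is added to SA1, and to any analysis that keeps participants with data on only one diet. SA4 and the all-time-points model should state whether they do.
- Such adjustment cannot alter the diet estimate in model (1) and will not be presented as a robustness check of it.

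The 0.8 threshold can stay. No new data are needed, as baseline HbA1c and diabetes status are already collected. In SA1 with 40 participants, the two fixed covariates reduce the residual degrees of freedom from 38 to 36. The expected number of further covariates triggered by chance is 10 × 0.0157 = 0.16 to 20 × 0.0157 = 0.31 for 10 to 20 characteristics. In return, SA1 is guarded against chance imbalance and will be more precise to the extent that the covariates predict the outcome; the SAP gives no figure from which to size that gain.

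### Adherence to the two diets is compared with Fisher's exact test, although the same crossover participants supply both rates

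*SAP*

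**What the plan says.** The Study Design section describes a two-period crossover. "Forty participants are planned to be randomized between the two arms"; one arm is to "start with 12 week WFKD and switch to 12 week Med-Plus", and the other takes the diets in reverse order.

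For adherence, the Primary Analysis section says the trial will "compare rate of adherence for WFKD after 12 weeks and Med-Plus diets after 12 weeks using a Fisher's Exact test", based on weekly dietary records. It continues: "We will develop a composite score to measure a participant's adherence to each diet". That is two adherence results per person, one for each diet.

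The same section treats other diet contrasts as paired. The HbA1c model includes order, diabetes status "and a random effect for each participant, i". For satisfaction, "we will use a Wilcoxon signed-rank test to evaluate the null hypothesis that the difference between pairs follows a symmetric distribution around zero".

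Fisher's test appears a second time in that section, for a difference in the "rate of adherence due to diabetes vs pre-diabetes status, within each diet". The section also states: "A significance level of 0.05 is set for all analyses".

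**The concern.** Fisher's exact test is a test for two separate groups of people. Here the same people appear in both rows of the table. The test sees how many were adherent on each diet, but not whether they were the same individuals, and that is the information a crossover is designed to provide.

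The direction of the error depends on how adherence on one diet relates to adherence on the other within a person. If people who keep to one diet tend to keep to the other (positive correlation), Fisher's test is too conservative and can miss a difference that the paired data show. If those who manage one diet tend to fail the other (clearly negative correlation), it can exceed the stated 0.05 level. At zero correlation it behaves much like exact McNemar.

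At stake is the reported p-value for whether one diet was followed better than the other, which bears on how readers interpret the HbA1c contrast. The HbA1c test and its adherence-adjusted sensitivity analysis do not use this p-value.

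**Working it through.** **Inputs.** From the SAP: 40 participants, each on both diets, so at most 40 pairs; significance level 0.05. Assumed, because the SAP gives no values: a two-sided test, one adherent/non-adherent result per person per diet, the adherence rates, and the within-person correlation φ. The SAP states no power or error rate for this comparison, so there is no figure of its own to reproduce.

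**Why φ matters.** The variance of the difference between the two observed rates is

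[p₁(1−p₁) + p₂(1−p₂) − 2φ√(p₁(1−p₁)p₂(1−p₂))] / n.

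An independent-groups test sets φ = 0. At 60% on each diet that gives (0.24 + 0.24)/40 = 0.0120. The true value is (0.48 − 0.144)/40 = 0.0084 at φ = 0.3, and (0.48 + 0.144)/40 = 0.0156 at φ = −0.3. Fisher's reference variance is therefore too large in the first case and too small in the second.

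**Exact error rates and power.** The four paired cells are: adherent on both, p₁₁ = p₁p₂ + φ√(p₁(1−p₁)p₂(1−p₂)); on WFKD only, p₁ − p₁₁; on Med-Plus only, p₂ − p₁₁; on neither, the remainder. All possible tables for n = 40 were enumerated with their multinomial probabilities, summing those with p ≤ 0.05.

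| Assumed rates (WFKD, Med-Plus) | φ | Fisher | Exact McNemar | Mid-p McNemar |
|---|---|---|---|---|
| 60%, 60% (type I error) | −0.3 | 5.7% | 3.0% | 4.4% |
| | 0 | 3.0% | 3.0% | 4.6% |
| | 0.3 | 1.0% | 2.6% | 4.5% |
| | 0.5 | 0.2% | 2.2% | 4.1% |
| 55%, 80% (power) | −0.2 | 58% | 50% | 57% |
| | 0 | 59% | 58% | 66% |
| | 0.1 | 59% | 63% | 70% |
| | 0.3 | 60% | 74% | 81% |
| | 0.5 | 62% | 91% | 95% |

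The last row is close to the largest correlation those rates allow, (0.55 − 0.44)/0.199 = 0.55, and should be read as an extreme. Over common rates of 50 to 80% and φ from −0.2 to 0.5, type I error runs 0.2–5.2% for Fisher, 1.4–3.0% for exact McNemar and 3.3–4.7% for mid-p McNemar.

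**One pair of totals, different data.** Take 22/40 adherent on one diet and 30/40 on the other. Fisher gives p = 0.10 whatever the pairing. McNemar uses the discordant pairs b and c: exact p = 2·P(X ≤ min(b,c)) with X ~ Binomial(b+c, ½), and mid-p subtracts P(X = min(b,c)). For 2 vs 10, exact p = 2(1 + 12 + 66)/4096 = 0.039, and mid-p = 0.039 − 66/4096 = 0.022.

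| Discordant pairs | φ in the table | Exact McNemar p | Mid-p |
|---|---|---|---|
| 0 vs 8 | 0.64 | 0.008 | 0.004 |
| 2 vs 10 | 0.41 | 0.039 | 0.022 |
| 3 vs 11 | 0.29 | 0.057 | 0.035 |
| 4 vs 12 | 0.17 | 0.077 | 0.049 |
| 10 vs 18 | −0.52 | 0.18 | 0.14 |

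**The case against.** The strongest objection is to weight. The comparison is not a listed outcome; the listed adherence outcome is diabetes vs pre-diabetes, where Fisher's test is appropriate. The risk of excess false positives is also small: in the 50–80% grid above, Fisher passes 5% only at 50% and φ = −0.2 (5.2%), and nothing in the SAP points to negative correlation. Both points stand, so the likely harm is lost power.

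Part of the mid-p gain is not due to pairing. At φ = 0 mid-p already beats Fisher by 7 points (66% vs 59%) because it is less conservative. For exact McNemar the gain is about 4 points at φ = 0.1 and 14 at 0.3. In the 22/40 vs 30/40 example, exact McNemar falls below 0.05 for only 3 of the 11 possible splits, those with φ of about 0.4 or more.

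McNemar has limits too. With no diet effect, 80% adherent in Phase I, 50% in Phase II and φ = 0.3, mid-p type I error is 2.3% with 20/20 per order, 3.2% with 22/18 and 5.9% with 24/16; exact McNemar at 24/16 is 3.5%. A large phase effect combined with clearly unequal orders can therefore disturb mid-p as well.

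Two readings might change the picture. The sentence could mean Phase I only, where the groups are separate, but nothing says so; the SAP states that restriction openly in its first sensitivity analysis, and the adherence score is per participant for each diet. If weekly records were instead pooled as separate observations, the figures above would not apply, but independence would fail further. Neither reading supports the test as written.

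**Conclusion.** The concern holds. The SAP applies a test for independent groups to paired data, out of line with its own paired handling of HbA1c and satisfaction. Fisher's actual type I error at a nominal 5% runs from about 0.2% to about 6% (5.7% at 60% adherence and φ = −0.3), depending on a correlation the test ignores. With moderate positive correlation (0.3) and 55% vs 80% adherence, it gives up 14 points of power to exact McNemar and 21 to mid-p.

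These sizes rest on assumed rates and correlations, 40 complete pairs, and one yes/no result per person per diet. That the test does not match the design rests on the SAP's text alone. The point should be corrected, but it concerns a supporting analysis and does not threaten the primary result.

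**What to change.** In the Primary Analysis section, replace Fisher's exact test for WFKD vs Med-Plus adherence with a two-sided McNemar test among participants with adherence data in both phases, using one adherent/non-adherent classification per participant per diet. Name either the mid-p or the exact version in advance. Mid-p stays closer to 5% and has more power; the exact version is the more cautious choice if a strong phase effect with unequal order groups is a worry.

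If a Phase I comparison was intended, say so; Fisher's test would then be valid. Keep Fisher's test for diabetes vs pre-diabetes within each diet.

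The cost is a change of SAP wording. No new data are needed, and no other analysis changes.
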